**Table HMGW.6.3 Secondary Efficacy Analysis**

Efficacy Variable	Derivation and Details	Analysis
1. Area under the curve of pain relief (AUC) a. BPI average pain severity	The relief score at a visit is defined as baseline score minus the BPI average pain score at the particular visit. The	Variable 1.a will be analyzed by the ANCOVA model described in Section

	area under the curve of relief (AUC) is the sum of each trapezoidal area circumscribed by the sides of relief scores at two consecutive non-missing visits and the side of days between the two visits.	6.1.2 and 6.1.3 (using baseline BPI average pain severity as covariate) for Study Period II.
2. Change from baseline to LOCF endpoint: a. BPI pain severity items: worst pain, least pain, average pain, and pain right now b. BPI-Interference items: general activity, mood, walking normally, normal work, relations with others, sleep, enjoyment of life, and school work (new item). c. BPI Average Interference score d. PPQ average pain, pain right now, and worst pain rating e. CGI-S: Mental Illness f. CGI-S: Overall Illness g. FDI-child h. FDI-parent i. CDI: total score j. MASC: total score, factor scores	a-b. eCRF data. c. Average of the non-missing ratings of the 8 individual items. d-f. eCRF data. g-h. FDI total score is the sum of 15 individual item scores. i. CDI total score is the sum of 27 individual item scores. j. MASC total score is the sum of 39 individual item scores ; the 4 factor scores are 1) physical symptoms, 2) social anxiety, 3) harm avoidance and 4) separation anxiety	The Variable 2.a to 2.j will be analyzed by the ANCOVA models as described in Section 6.1.2 and 6.1.3 for Study Period II.
3. Change from baseline to BOCF endpoint: a. BPI average pain severity b. PPQ average pain rating	a-b. eCRF data.	The Variable 3.a to 3.b will be analyzed by the ANCOVA models as described in Section 6.1.2 and 6.1.3 for Study Period II.
4. Change from baseline to each post-baseline visit: a. BPI pain severity items: worst pain, least pain, and pain right now b. BPI-Interference items: general activity, mood, walking normally, normal work, relations with others, sleep, enjoyment of life, and school work (new item). c. BPI Average Interference score d. CGI-Severity: Overall Illness e. CGI-Severity: Mental Illness	a-b. eCRF data. c. Average of the non-missing ratings of the 8 individual items. d-e. eCRF data.	Variables 4.a to 4.e will be analyzed by a repeated measures analysis as described in Section 6.1.2 and 6.1.3 for Study Period II.
5. Categorical variable: a. 30% Response rate (LOCF) b. 30% Response rate (BOCF) c. 50% Response rate (LOCF) d. 50% Response rate (BOCF) e. 30% Response rate (MMRM-	a-b. Response: at least 30% reduction from baseline to endpoint (LOCF or BOCF) for BPI average pain score. c-d. Response: at least 50% reduction from baseline to endpoint (LOCF or BOCF) for BPI average pain score.	For Variables 5.a to 5.d, and 5.g, proportions will be summarized by treatment group and will be analyzed by Fisher's exact test and CMH test controlling for


CAT)  f. 50% Response rate (MMRM-CAT)  g. Sustained response rate  h. Cumulative distribution of BPI average pain score reduction (BOCF)
	
e. Response at each post-baseline visit: at least 30% reduction from baseline.  f. Response at each post-baseline visit: at least 50% reduction from baseline.  g. Sustained response: at least 30% reduction from baseline to endpoint; with a 30% reduction from baseline at an earlier visit than the last visit, and remains at least 20% reduction from baseline in every visit in between, if there are any intervening visits (based on BPI average pain score). The sustained response analyses will include patients with both a baseline and at least two post-baseline values for BPI average pain score. h. The percentage of patients who have reached each threshold of BPI average pain reduction from baseline to BOCF endpoint (from >0% to 100% with a 10% increase) will be calculated. Discontinued patients will be considered as “no change”.
	
pooled investigative site for Study Period II.   For Variable 5.e and 5.f, the categorical, pseudo-likelihood-based repeated measures (MMRM-CAT) analysis will be used. See section 6.1.2 for details.   For Variable 5.h, the treatment group difference in the empirical cumulative distribution of the percentage pain reduction will be evaluated using Van der Waerden test for Study Period II.


6. Time to event variable:  a. Time to first 30% reduction in BPI average pain score  b. Time to first 50% reduction in BPI average pain score  c. Time to sustained response
	
a. For the patients with a 30% reduction at a visit in the treatment phase in SP II, time = days from the date of the visit that the earliest 30% reduction is observed to the date of the first day of SP II. The date of the first day of SP II is the randomization date.  b. For the patients with a 50% reduction at a visit in the treatment phase in SP II, time = days from the date of the visit that the earliest 50% reduction is observed to the date of the first day of SP II.  c. For the sustained responders defined above in SP II, time = the days from the date of the visit which is the earlier visit from which the sustained response is observed to the date of the first day of SP II.
	
For Variables 6.a to 6.c, the Kaplan-Meier survival curves of time to event will be calculated by treatment group for Study Period II. In the calculation, patients who do not have the event will be considered as right-censored observation. The comparison of the survival curves between treatment groups will be conducted by a log-rank test and stratified log-rank test controlling for pooled investigator.

Abbreviations: ANCOVA = analysis of covariance; BOCF = baseline observation carried forward; BPI = Brief Pain Inventory-Adolescent Version; CDI = Children's Depression Inventory; CGI-S = Clinical Global Impressions of Severity; eCRF = electronic case report form; FDI = Functional Disability Inventory; LOCF = last observation carried forward; MASC = Multidimensional Anxiety Scale for Children; PPQ = Pediatric Pain Questionnaire.

The treatment-by-investigator interaction will be tested using an ANCOVA model. When the interaction is statistically significant, the nature of the interaction will be investigated.

Descriptive statistics will be used to summarize all variables presented in HMGW.6.3 except variables 3a-b, 5(b, d, h) and 6a-c by treatment group for all ITT patients entering Study Period III. Descriptive statistics will be used to summarize variables 1a, 2a-f, and 4a-e for Study Period II/III. For continuous measures, when appropriate, within treatment testing of change from baseline will be conducted for SP III and SP II/III.

For efficacy measures, data from all visits will be listed.

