#### 6.1.2. General Considerations

Efficacy and safety analyses will be done on an intent-to-treat (ITT) basis unless otherwise specified. An intent-to-treat analysis is an analysis of data by the groups to which patients are assigned by random allocation, even if the patient does not take the assigned treatment, does not receive the correct treatment, or otherwise does not follow the protocol.

All efficacy and safety analyses of continuous measures will include randomized patients with both a baseline and at least one post-baseline value for the variable being analyzed. For efficacy and continuous safety variables, baseline is defined as the last measurement taken at, or prior to the visit where the study period begins; endpoint is defined as the last non-missing measurement for the study period of interest. Table HMGW 6.1 provides baseline and post-baseline definitions for all variables.

Statistical analyses will be carried out for Study Period II, III, and IV (SP II-IV). All tests of hypotheses will be evaluated based on a two-sided significance level of 0.05 unless otherwise specified. No adjustments for multiple comparisons will be made.

For SP II, a patient's treatment group will be determined by the treatment to which the patient is randomized: either duloxetine (DLX) or placebo (PLA).

For SP III, the following treatment groups will be determined by the randomized treatment at SP II and extension phase treatment at SP III:

PLA/DLX: patients who are randomized to placebo at SP II and who enter SP III and take duloxetine.

DLX/DLX: patients who are randomized to duloxetine at SP II and who enter SP III and take duloxetine.

No statistical comparisons will be conducted to compare the two treatment groups PLA/DLX and DLX/DLX during SP III unless otherwise noted. For continuous measures, when appropriate, within treatment testing of change from baseline for selected safety and efficacy measures will be conducted for SP III.

For SP II/III, one treatment group will be determined by the randomized treatment at SP II:

DLX: patients who are randomized to duloxetine at SPII, including patients who may have discontinued early at SPII or who enter SPIII.

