**Table HMGW.6.1 Patient Population with Baseline and Post-baseline Definitions by Study Period and Type of Analysis**

Study Period / Analysis	Patient Population	Baseline Definition	Post-baseline Definition
Acute Phase			
Efficacy	Patients with a baseline and at least one post-baseline observation	Last of Visits 1-2	All Visits 3-8
TEAEs	All randomized patients	All Visits 1-2	All Visits 2.01-8
SAE and DCAE	All randomized patients	NA	All Visits 2.01-8
C-SSRS categorical analyses	All randomized patients	Lifetime baseline: All Visits 1-2 Lead-in baseline: Visit 2	All Visits 2.01-8
Treatment Emergent Abnormal Labs	Patients with normal laboratory values at all nonmissing baseline visits (with respect to direction being analyzed) and who have at least one post-baseline observation	All of Visits 1-2	All Visits 2.01-8
Treatment emergent low blood pressure	Patients with normal values at all nonmissing baseline visits (with respect to direction being analyzed) and who have at least one post-baseline observation. See Table HMGW.6.4 for normal limits of blood pressure.	Minimum value from Visits 1-2	All Visits 2.01-8
PCS in vital signs, weight, sustained blood pressure analyses	Vital signs: Patients with normal values at all nonmissing baseline visits (with respect to direction being analyzed) and who have at least one post-baseline observation. See Table HMGW.6.4 for normal limits of vital signs. Weight:	Low: Minimum value from Visits 1-2 High: Maximum value from Visits 1-2	All Visits 2.01-8

	Patients with non-missing baseline and at least one post-baseline value.		
Treatment-emergent changes in ECG intervals and heart rate	Patients with normal values at all nonmissing baseline visits (with respect to direction being analyzed) and who have at least one post-baseline observation. See Table HMGW.6.8 for normal limits of ECG.	Low: Minimum value from Visits 1-2 High: Maximum value from Visits 1-2	All Visits 2.01-8
Continuous Safety measures	Patients with a baseline and at least one post-baseline observation	Last of Visits 1-2	All Visits 3-8
Extension Phase			
Efficacy	Patients with a baseline and at least one post-baseline observation	Last of Visits 3-8	All Visits 9-15
TEAEs	All randomized patients entering extension phase	Maximum severity between $7 \leq \text{Visit} \leq 8$	All Visits 8.01-15
SAE and DCAE	All randomized patients entering extension phase	NA	All Visits 8.01-15

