### **6.1.3. Adjustments for Covariates**

In general, when a repeated measures analysis is used, the model will include the fixed categorical effect of treatment, pooled investigative site, visit, treatment-by-visit interaction, and the continuous, fixed covariates of the baseline value of the variable being analyzed and baseline value of the variable being analyzed-by-visit interaction. The baseline value of the variable being analyzed and the baseline value of the variable being analyzed-by-visit interaction are included to account for the differing influence over time of the baseline score on the post-baseline scores.

When an analysis of covariance (ANCOVA) model is used to analyze a continuous variable, the model will contain the main effects of treatment, pooled investigative site, and appropriate baseline values included as covariates.

Data presentations for Study Period III will be based on the same MMRM and ANCOVA models excluding treatment effect, where appropriate.

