Study Conduct - Compliance	
Randomized patient took <80% or >120% of study drug for >= 2 visit intervals
	
For randomized patients, if <80% or >120% of study drug is taken >= 2 visits (consecutive or non-consecutive), then result is protocol deviation.

Study Conduct – Key measurements not collected	Missing key efficacy measurement: <BPI average pain score, CGI-S overall illness>	For randomized patients, if BPI average pain severity or CGI-S overall illness is missing at any scheduled visit, then result is protocol deviation. Provide one record per patient per missing measurement per visit.
	Missing safety measurement: <CSSRS, Blood Pressure, Pulse, Height, Weight, Labs, ECGs>	For randomized patients, if C-SSRS, blood pressure, pulse, height, weight, are missing at any scheduled baseline or post-baseline visits at or before the early discontinuation visit, then result is protocol deviation. Provide one record per patient per missing measurement per visit.  For ALT lab test, if any scheduled or unscheduled baseline labs are missing or if a patient discontinued at or after visit 6 (the first scheduled post-baseline visit for labs is visit 6), and without any scheduled or unscheduled post-baseline labs data, then it is a protocol deviation.  For ECG QTcF measure, if any scheduled or unscheduled baseline ECGs are missing or if a patient discontinued at or after visit 8 (the first scheduled post-baseline visit is visit 8), and without any post-baseline data, then it is a protocol deviation.
Visit interval outside specified limits	Visit interval length exceeds (number of days study drug dispensed + 2 days) (excluding taper phase)	For randomized patients, compare actual visit interval length to number of days study drug dispensed at each visit. Allowable visit interval lengths (resulting in no more than 2 days off drug):  Visit 2,3, 8: 11 days  Visit 4, 9: 20 days  Visit 5,6,7, 10: 29 days  Visit 11: 38 days  Visit 12,13: 47 days

		Visit 14: 56 days
--	--	-------------------

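### The AUC of pain relief (variable 1.a) is a sum of point-days over each patient's own observation time, so its comparison between arms mixes relief with length of follow-up

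*SAP*

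**What the plan says.** SAP Table HMGW.6.3, variable 1.a, builds the measure in two steps. First: "The relief score at a visit is defined as baseline score minus the BPI average pain score at the particular visit". Improvement is therefore positive and worsening negative. Then the "area under the curve of relief (AUC) is the sum of each trapezoidal area circumscribed by the sides of relief scores" taken "at two consecutive non-missing visits and the side of days between the two visits". The unit is BPI points times days.

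The same row assigns the variable to the ANCOVA of Sections 6.1.2 and 6.1.3, with baseline BPI average pain as covariate. Section 6.1.3 says "the model will contain the main effects of treatment, pooled investigative site, and appropriate baseline values included as covariates". No term represents time observed.

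Table HMGW.6.1 sets the efficacy population: "Patients with a baseline and at least one post-baseline observation". One post-baseline score is enough, so early leavers are included. Section 5.2 plans on about 81% completing Study Period II.

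After Table HMGW.6.3, Section 6.1.13.2 adds a second use: "Descriptive statistics will be used to summarize variables 1a, 2a-f, and 4a-e for Study Period II/III". Section 6.1.2 defines the single duloxetine group for that combined period as "including patients who may have discontinued early at SPII or who enter SPIII".

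**The concern.** An undivided area grows with the time over which it is summed. Two patients with the same relief get different scores if one was followed for longer. Retention can differ between arms, so a difference in dropout can appear as a difference in pain relief, or can hide one.

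No other rule in the SAP closes the gap. The LOCF and BOCF rules in Section 6.1.2 define endpoint values. The carry-forward of early-discontinuation data in the same section applies to repeated measures analyses only. As written, time after the last visit adds nothing to the AUC, which is the same as assigning zero relief. That lowers the score of a patient who was improving and raises the score of one who was getting worse, so the distortion has no fixed direction.

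**Working it through.** The SAP states no figure for the AUC, so there is none to reproduce.

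**Inputs**
- Nominal visit days 0, 7, 14, 28, 49, 70, 91 for Visits 2 to 8. These are inferred, because the SAP does not list them. Section 5.1 puts Visit 8 at Week 13 and Visit 9 at Week 14, a 7-day step, and gives the first dose step as 1 week. Table HMGW.6.2 gives the limits "Visit 2,3, 8: 11 days", then 20 days for Visit 4 and 29 days for Visits 5 to 7. Reading these as 7-, 14- and 21-day steps gives 7 + 7 + 14 + 21 + 21 + 21 = 91 days, which is 13 weeks.
- Baseline (relief 0) is taken as the start of the first trapezoid. The SAP does not say so.
- Relief profiles and dropout patterns are illustrative assumptions.

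**Single patients.** For constant relief r from Visit 3 and last visit on day T, AUC = 7 × r/2 + (T − 7) × r = r × (T − 3.5).

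| Profile | Last visit | AUC (point-days) | AUC ÷ days |
|---|---|---|---|
| +2 | day 91 | 2 × 87.5 = 175 | 1.92 |
| +2 | day 28 | 2 × 24.5 = 49 | 1.75 |
| +3 | day 28 | 3 × 24.5 = 73.5 | 2.62 |
| +1 | day 91 | 1 × 87.5 = 87.5 | 0.96 |
| −1 | day 91 | −87.5 | −0.96 |
| −1 | day 28 | −24.5 | −0.88 |

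Rows 1 and 2 show the same relief with a 3.6-fold gap (175/49). Rows 3 and 4 show a reversed ranking: 3-point relief to Week 4 scores below 1-point relief in a completer. Division restores the order.

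If baseline is not counted, the first trapezoid drops out. Constant +2 then gives 168 against 42, and a patient with one post-baseline visit has no trapezoid at all.

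**Two arms, equal true relief of 2 points, completion 86% against 76%** (average 81%, as planned)
- All dropouts at Week 4: 0.86 × 175 + 0.14 × 49 = 157.4; 0.76 × 175 + 0.24 × 49 = 144.8. The false difference is 12.6 point-days.
- Dropouts spread evenly over Visits 3 to 7: their mean AUC is (7 + 21 + 49 + 91 + 133)/5 = 60.2. The false difference is 0.10 × (175 − 60.2) = 11.5 point-days.
- Standardised: take a between-patient SD of relief of 2.2. The SAP gives none; 184 patients at 81% completion would imply about 2.18 if only completers count. A simulation with 400,000 patients per arm then gives about 0.06 SD. At 92 per arm the standard error of a standardised difference is about √(2/92) = 0.147, so the shift is 0.062/0.147 = 0.4 SE.
- With 9% against 29% dropout, the difference is 0.20 × 114.8 = 23 point-days, about 0.12 SD.
- Direction: if mean relief is −1, dropouts average −30.1 and completers −87.5. The difference is then 0.10 × 57.4 = 5.7 point-days in favour of the arm with more dropout.

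**After division.** In the same simulation the standardised differences fall from 0.062 to 0.015 (14% against 24%) and from 0.124 to 0.030 (9% against 29%).

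**Combined Study Period II/III.** Constant +2 over 39 weeks (273 days) gives 2 × 269.5 = 539, against 49 for a Week 4 leaver: 11-fold for equal relief, within one summarised group.

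**The case against.** The best defence is that the undivided sum is a legitimate quantity: total relief accrued on study, with no credit after leaving. The SAP uses that principle in its BOCF endpoint, and for variable 5.h it counts discontinued patients as unchanged. For a patient with net relief it is conservative. But the SAP writes the rule out in those places and not for 1.a, and for a patient who is worsening it is not conservative.

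The size also needs scale, and here the objection largely stands. The design difference of 1.0 point, if constant from Visit 3, is worth 87.5 point-days. An artefact of 11 to 13 is small beside it and beside the sampling error. AUC is not among the secondary objectives in Section 4.2, the same BPI item is analysed in several other ways, and discontinuation reasons and exposure are compared between arms separately, so differential retention would be visible.

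Three stronger readings are tempting but not supported:
- **That division stops a worsening patient from gaining by leaving early.** It does not. With linear worsening to −2 by day 91, the divided AUC is −1.00 for a completer and −0.31 for a patient leaving at day 28. That is informative dropout, which rescaling cannot remove.
- **That stretched visits bias the comparison.** The limits in Table HMGW.6.2 sum to 11 + 11 + 20 + 29 + 29 + 29 = 129 days against 91. They are thresholds for flagging deviations, hence an outer bound, and nothing suggests that they would be reached unequally in a double-blind period. Equal stretching adds noise.
- **That the Study Period II/III AUC mainly measures retention.** No calculation shows this, and with one group there is no comparison between arms to bias.

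**Conclusion.** The point holds as a minor correction to one secondary variable. As defined, variable 1.a cannot separate how much relief a patient had from how long the patient was observed, and the Study Period II ANCOVA inherits this. Under equal 2-point relief and a 10-percentage-point gap in dropout, the false difference is about 11 to 13 point-days, or 0.06 SD; it roughly doubles with a 20-point gap. If dropout is equal in both arms and unrelated to relief, no false difference arises under equal true relief. The figures rest on the inferred visit days, constant relief from Visit 3, dropout unrelated to relief, and the assumed SD of 2.2.

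The combined-period summary is hard to interpret, because it adds up areas over anything from days to 39 weeks, but it carries no bias between arms. The primary MMRM and the sample size do not depend on this variable.

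**What to change.** In Table HMGW.6.3, variable 1.a:
- Divide each patient's AUC by the days from baseline to that patient's last non-missing visit in the period. The result is time-weighted mean relief in BPI points.
- State that baseline, with relief 0, starts the first trapezoid.
- Keep the same ANCOVA for Study Period II, and summarise the divided measure for Study Periods III and II/III.
- State that the change removes the dependence on follow-up length but not informative dropout, and that BOCF variable 3.a remains the counterpart that gives no credit after dropout.

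The cost is a few lines of SAP text and a small programming change. The downside is that a short-stay patient's brief relief gets the same weight as a completer's, as LOCF variable 2.a already allows. The SAP already averages this way elsewhere: the mean daily dose in Section 6.1.10 is weighted by days and divided by total days.

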### 4.2. Secondary Objectives

The secondary objectives of the study are as follows:

- To evaluate the efficacy of duloxetine 30/60 mg QD in the treatment of adolescents with JPFS during a 13-week, double-blind treatment phase, based on the improvement of the following measures:
  - Brief Pain Inventory (BPI) Modified Short Form: Adolescent Version severity (worst pain, least pain, pain right now) and interference.
  - Response to treatment, as defined by a 30% and 50% reduction in the BPI average pain severity.
  - Pediatric Pain Questionnaire (PPQ) pain right now, worst pain and average pain items.
  - Clinical Global Impression of Severity for Overall Illness (CGI-Severity: Overall Illness) scale.
  - Clinical Global Impression of Severity for Mental Illness (CGI-Severity: Mental Illness) scale.
  - Functional Disability Inventory - child version scale (FDI-child).
  - Functional Disability Inventory - parent version scale (FDI-parent).
  - Children's Depression Inventory (CDI).
  - Multidimensional Anxiety Scale for Children (MASC).
- To evaluate the safety and tolerability of duloxetine 30/60 mg QD in the treatment of adolescents with JPFS during a 13-week, double-blind treatment phase.
- To evaluate the efficacy and safety of duloxetine 30/60 mg QD during a 26-week, open-label, extension treatment phase, as assessed by the following:
  - Maintenance effect of duloxetine 30/60 mg QD during the open-label extension treatment phase. Maintenance effect will be assessed using the BPI average pain severity in only the duloxetine treated acute phase responders (defined as those patients with  $\geq 30\%$  pain reduction from baseline on the BPI average pain severity measure at the last non-missing assessment in Study Period II).
  - Effect of duloxetine 30/60 mg QD during an extension treatment phase as measured by the following: BPI, PPQ, CGI-Severity: Overall Illness, CGI-Severity: Mental Illness, FDI-child, FDI-parent, CDI, and MASC.

- Safety of duloxetine 30/60 mg QD during an extension treatment phase.

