#### **6.1.4. Handling of Dropouts or Missing Data**

Missing efficacy and safety data can occur for multiple reasons, including missed patient visits (for example, patients discontinuing from the study early) and scales or measures with missing item scores.

When change from baseline is assessed, only patients with a baseline and at least one post-baseline measurement will be included in the analyses.

For the repeated measures analyses, the model parameters are simultaneously estimated using restricted likelihood estimation incorporating all of the observed data.

Unless otherwise specified, when a total score or an average score is calculated from individual items, it will be considered missing if any of the individual items are missing.

For the assessment of efficacy, handling of missing data depends on the missing data mechanism assumptions. There are three missing data mechanisms: 1) missing completely at random (MCAR), 2) missing at random (MAR) and 3) missing not at random (MNAR). Three primary statistical approaches to handling missing data will be utilized: mixed model repeated measures (MMRM) analyses, ANCOVA/ANOVA using last observation carried forward (LOCF) change from baseline to endpoint, and ANCOVA/ANOVA using baseline observation carried forward (BOCF) change from baseline to endpoint. The LOCF and BOCF imputation methods in general make MNAR assumption, while the repeated measures analysis assumes MAR. A sensitivity analysis will be performed to assess the impact of missing data assumptions on the primary analysis conclusions (see section 6.1.13.3 for details).

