### **6.3. Exploratory Objective Analyses**

#### **6.3.1. Correlation between Pediatric Pain Questionnaire and Brief Pain Inventory**

The correlation between PPQ and BPI for each item (average pain rating, pain right now rating, worst pain rating) will be assessed. The correlation for all records where both PPQ and BPI data are non-missing at visits across the entire study for all ITT will be assessed by using Pearson's correlation coefficient.

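### PPQ, FDI, CDI and MASC are secondary objectives, but Table HMGW.6.3 gives them no repeated measures comparison in Study Period II, only LOCF ANCOVA (plus BOCF for PPQ average pain)

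*SAP*

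**What the plan says.** SAP Section 4.2 lists "Pediatric Pain Questionnaire (PPQ) pain right now, worst pain and average pain items" among the secondary efficacy measures of the 13-week double-blind phase. It also lists FDI-child, FDI-parent, CDI and "Multidimensional Anxiety Scale for Children (MASC").

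Table HMGW.6.3 assigns the Study Period II methods:

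- **Row 2, "Change from baseline to LOCF endpoint".** This holds BPI severity and interference, both CGI-S scales, PPQ (2.d: "PPQ average pain, pain right now, and worst pain rating"), FDI-child and FDI-parent (2.g, 2.h), CDI (2.i) and MASC (2.j). The method is stated as "The Variable 2.a to 2.j will be analyzed by the ANCOVA models as described in Section 6.1.2 and 6.1.3 for Study Period II".
- **Row 3, BOCF.** BPI average pain (3.a) and PPQ average pain (3.b) only.
- **Row 4, "Change from baseline to each post-baseline visit".** BPI worst, least and current pain, BPI interference, and the two CGI-S scales, by repeated measures. BPI average pain has its MMRM as the primary analysis (Section 6.1.13.1).

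Section 6.1.4 describes the assumptions: "The LOCF and BOCF imputation methods in general make MNAR assumption, while the repeated measures analysis assumes MAR". Section 6.1.2 sets the Study Period II LOCF endpoint as the last available value from Visit 3 through Visit 8. The delta-based sensitivity analysis in Section 6.1.13.3 concerns the primary analysis only.

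**The concern.** Every BPI and CGI-S measure gets an MMRM as well as an LOCF analysis. The other named secondary scales do not, and the SAP gives no reason. For FDI, CDI, MASC and two of the three PPQ items, the LOCF ANCOVA is the only planned between-arm result in Study Period II. For PPQ average pain the only alternative is BOCF, which Section 6.1.4 puts in the same class of assumption.

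An LOCF mean mixes Week 13 values from completers with earlier values from patients who left. If scores are still improving when patients leave, the between-arm difference depends on how many leave each arm and when. Unequal dropout can then shrink a real difference or create one where none exists. Nothing planned for these scales would show that this had happened.

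Sparse collection does not by itself explain the omission. Section 6.1.2 already has an MMRM rule for variables not collected at every visit: a value from an early discontinuation visit is moved to the next scheduled collection visit.

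**Working it through.** **The plan's own figures.** Section 5.2 gives 184 patients, 1:1, and about 81% completion, so average dropout is 1 - 0.81 = 19%. The SAP states no SD, so 184 cannot be reproduced, and this point does not depend on it. Purely to scale the results, the SD can be back-solved from 80% power, a difference of 1.0, two-sided alpha 0.05 and 184 x 0.81 / 2 = 74.5 completers per arm: 1.0 / [(1.960 + 0.842) x sqrt(2/74.5)] = 2.18. With 92 per arm the standard error of a difference is 2.18 x sqrt(2/92) = 0.32.

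**Assumptions not in the SAP.** Scores at Weeks 1, 2, 4, 7, 10 and 13. Improvement follows 1 - exp(-week/4). Dropout is unrelated to outcome. The week 13 placebo change is -1.5 where there is a true difference; where there is none, both arms change by -2. The arm-specific dropout rates are also assumed, chosen to average 19%.

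**Formula.** Let d be an arm's dropout, m its Week 13 mean change, and F the average fraction of m reached at the last observed visit among dropouts. The expected LOCF mean is m x [1 - d(1 - F)].

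The fraction of the Week 13 change reached at Weeks 1, 2, 4, 7 and 10 is 0.230, 0.409, 0.658, 0.860 and 0.955.

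- Last visits spread evenly: F = 0.622, 1 - F = 0.378.
- Last visits weighted early (30, 30, 20, 10, 10%): F = 0.505, 1 - F = 0.495.

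**Worked case, 24% duloxetine and 14% placebo, true difference -1.0, even spread.** Duloxetine: -2.5 x (1 - 0.24 x 0.378) = -2.273. Placebo: -1.5 x (1 - 0.14 x 0.378) = -1.421. LOCF difference: -0.85. With early weighting: -2.203 + 1.396 = -0.81.

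| Dropout, placebo vs duloxetine | True difference -1.0 reads | No true difference reads |
|---|---|---|
| 19% vs 19% | -0.91 to -0.93 | 0 |
| 14% vs 24% | -0.81 to -0.85 | +0.08 to +0.10 |
| 10% vs 28% | -0.73 to -0.79 | +0.14 to +0.18 |

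No-effect check: 2 x (0.24 - 0.14) x 0.378 = 0.08, and with 0.495 it is 0.10. On the scale above, 0.08 to 0.18 is 0.25 to 0.56 standard errors.

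**Outcome-dependent (MAR) dropout.** A simulation with 92 per arm assumed a linear time course, placebo change -1.5, SD 2.2, correlation 0.6 between visits, and dropout more likely after a worse score. For a true -1.0, LOCF averaged -0.84 (duloxetine 18% vs placebo 17%), -0.58 (25% vs 12%) and -1.14 (12% vs 25%). With no effect it averaged +0.28 (28% vs 12%) and -0.20 (13% vs 25%). A MAR likelihood-type estimate stayed within 0.01 of the truth throughout. That follows from how dropout was generated, so it does not show how an MMRM would behave under missing not at random.

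**The case against.** **The collection schedule is not in the SAP.** This is the strongest point against. Section 6.3.1 correlates PPQ and BPI wherever both are "non-missing at visits across the entire study for all ITT". A reader might infer repeated PPQ collection within Study Period II. The sentence does not establish it: the pool includes baseline and the extension, so PPQ at baseline, Visit 8 and Visit 15 would fit equally well. For FDI, CDI and MASC there is no sign of repeated collection. Section 6.1.13.2 leaves these scales (2.g to 2.j) out of the combined Study Period II/III summaries. With a single scheduled collection, the carry-forward rule in Section 6.1.2 would make an MMRM nearly the same as LOCF ANCOVA. This stands, and the fix is conditional because of it.

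**Like-for-like comparisons exist.** A reader might infer that PPQ results cannot be interpreted beside BPI, or that a disagreement could not be traced to method or scale. The documents do not support that. BPI average, worst and current pain have the same LOCF ANCOVA (2.a) as the PPQ items (2.d), and both average pain items have BOCF (3.a, 3.b). BPI by LOCF against BPI by MMRM would show the effect of method.

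**The size is modest and assumed.** With equal dropout and no effect the closed form gives zero. With more dropout on duloxetine the shift goes against the drug, and the opposite imbalance reverses the no-effect shift. This stands.

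**LOCF is pre-specified and its assumption disclosed.** True, and these are unadjusted secondary endpoints. But disclosure does not explain why some secondary scales get an MMRM and others do not.

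**Conclusion.** The gap is on the face of the table: PPQ, FDI-child, FDI-parent, CDI and MASC have no MAR-based between-arm estimate in Study Period II, whereas every BPI and CGI-S measure does. It should be closed wherever the collection schedule allows.

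Whether the LOCF results will in fact be distorted is unknown, because the SAP gives neither dropout by arm nor a time course. At 14% versus 24% dropout the illustration shows a loss of about 0.15 to 0.19 from a true 1.0, or a spurious difference of about 0.1 where none exists. Both depend on the assumed visits and dropout split. The primary conclusion is unaffected.

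**What to change.** - Add the three PPQ items to variable 4 of Table HMGW.6.3. Add FDI-child, FDI-parent, CDI and MASC wherever they have more than one scheduled post-baseline collection in Study Period II. Apply the existing Section 6.1.2 rule for variables not collected at every visit.
- For the measures added, state that the Visit 8 MMRM contrast is the main comparison, and keep LOCF (and BOCF for PPQ average pain) as supportive.
- Where a scale has only one scheduled collection, leave the LOCF ANCOVA as it is. An ANCOVA restricted to observed Visit 8 values is not a good substitute, since it analyses completers and brings its own selection.

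Cost: wording in one table and a few extra models and tables that reuse the BPI code.
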